## ANNEX 1. LIST OF STANDALONE DOCUMENTS

Not applicable.

## ANNEX 2. ADDITIONAL INFORMATION

### Rules for Defining Change in Therapy Line

Condition	Rule
Switch to a completely new agent or combination of agents	Change in therapy line
Switching between CDK4/6 inhibitors (e.g., palbociclib to ribociclib or abemaciclib)	Change in therapy line
Therapy suspended for greater than 90 days	Change in therapy line
Addition of a new agent to an existing treatment regimen*	Change in therapy line
Removal of an agent from a combination regimen	Not a change in therapy line
Exception to switching within the same treatment class	
Anastrozole to letrozole (or vice versa)	Not a change in therapy line
Anastrozole to exemestane (or vice versa)	Not a change in therapy line
Letrozole to exemestane (or vice versa)	Not a change in therapy line

1L = first line; CDK4/6 = cyclin-dependent kinase 4 and 6.

\*A treatment regimen is defined as combination of all agents administered within a 30-day period from the date of initiation of the first agent, with the exception of CDK4/6 inhibitors, for which a 60-day period will be allowed to account for insurance coverage delays. Addition of a new agent after 30 days (or 60 days for CDK4/6 inhibitors) will be considered a change in therapy line. A given therapy line will be considered to have ended upon occurrence of the earliest of any of the following: switch to a new treatment regimen or a gap of more than 90 days in administration or refill of any of the 1L regimen drugs.

PFIZER CONFIDENTIAL

## List of Systemic Therapy Agents

Therapy agents	HCPCS codes
CDK4/6 inhibitors	
Palbociclib	N/A
Ribociclib	N/A
Abemaciclib	N/A
Aromatase inhibitors	
Anastrozole	S0170
Letrozole	N/A
Exemestane	S0156
Other hormonal therapy	
Fulvestrant	J9393, J9394, J9395, C9120
Tamoxifen	S0187
Toremifene	N/A
Kinase inhibitor	
Everolimus	J7527, J8561
Specific chemotherapy agents	
Doxorubicin (all forms)	C9415, J9000, J9001, J9002, Q2048, Q2049, Q2050
Epirubicin	C1167, J9178, J9180
Eribulin	C9280, J9179
Gemcitabine	J9198, J9201
Capecitabine	J8520, J8521
Docetaxel	J9170, J9171
Paclitaxel (all forms)	C9127, C9431, J9264, J9265, J9267, J9259
Cyclophosphamide	C9420, C9087, C9421, J8530, J9070, J9071, J9080, J9090, J9091, J9092, J9093, J9094, J9095, J9096, J9097
Fluorouracil	J9190
Cisplatin	C9418, J9060, J9062
Carboplatin	J9045

PFIZER CONFIDENTIAL

Therapy agents	HCPCS codes
Oxaliplatin	C9205, J9263
Methotrexate	J8610, J9250, J9260
Vinorelbine	C9440, J9390
Vinblastine	J9360
Leuprolide	C9430, J1950, J9217, J9218, J9219, J1952
Irinotecan	C9474, J9205, J9206
Ixabepilone	C9240, J9207
Etoposide	C9414, C9425, J8560, J9181, J9182
Mitomycin	C9432, J9280, J9290, J9291, J9281, C9064
NOS chemotherapy agent	J8999, J9999
Other targeted therapies	
Olaparib	N/A
Alpelisib	N/A
Lapatinib	N/A
Tucatinib	N/A
Neratinib	N/A
Larotrectinib	N/A
Entrectinib	N/A
Talazoparib	N/A
Trastuzumab (all forms)	C9131, J9316, J9354, J9355, J9356, J9358, Q5112, Q5113, Q5114, Q5116, Q5117
Pertuzumab	C9292, J9306, J9316
Bevacizumab	Q2024, C9257, C9214, Q5118, Q5107, C9142, Q5126, Q5129, S0116, J9035
Pembrolizumab	C9027, J9271
Atezolizumab	C9483, J9022
Sacituzumab	C9066, J9317
Nivolumab	C9453, J9299, J9298

PFIZER CONFIDENTIAL

CDK4/6 = cyclin-dependent kinase 4 and 6; HCPCS = Healthcare Common Procedure Coding System; N/A = not available; NOS = not otherwise specified.

Note: All treatments will be identified using a combination of HCPCS codes and the generic drug names in the Medicare Prescription Drug Event file that are linked to corresponding National Drug Codes assigned to each drug. Treatments with no applicable HCPCS codes will only be identified using generic drug names.

PFIZER CONFIDENTIAL

PSM	propensity score matching
RPSFT	Rank Preserving Structural Failure Time
SEER	Surveillance, Epidemiology, and End Results
sIPTW	stabilized inverse probability of treatment weighting
SSA	Social Security Administration
CCI	
US	United States

PFIZER CONFIDENTIAL

CT24-WI-GL03-RF03 2.0 Non-Interventional Statistical Analysis Plan For Secondary Data Collection Study

01-Jun-2020

Page 3 of 29

1 AMENDMENTS FROM PREVIOUS VERSION(S)

Not applicable

2 INTRODUCTION

Nearly 70% of all metastatic breast cancer (mBC) cases are of the hormone receptor-positive (HR+)/human epidermal growth factor receptor 2-negative (HER2-) subtype. Endocrine therapies (ETs), such as aromatase inhibitors (AIs), tamoxifen, and fulvestrant, have remained the mainstay of therapy for patients with HR+/HER2- mBC for nearly 2 decades; however, in recent years, several newer targeted therapies, particularly the class of cyclin-dependent kinase 4 and 6 (CDK4/6) inhibitors, have become available: palbociclib (February 2015), ribociclib (March 2017), and abemaciclib (September 2017). Phase 3 clinical studies have shown that CDK4/6 inhibitors used in combination with an AI in first line (1L) in HR+/HER2- mBC significantly increased progression-free survival compared with AI monotherapy. However, evidence on the secondary endpoint of overall survival (OS) from the clinical studies is mixed across different CDK4/6 inhibitors. In the phase 3 trial PALOMA-2, palbociclib + letrozole in the 1L setting demonstrated a numerical improvement but not a statistically significant OS increase, with median OS of 53.9 months for palbociclib + letrozole versus 51.2 months for letrozole alone (hazard ratio, 0.956; 95% confidence interval [CI], 0.78-1.18) (Finn et al., 2022). Likewise, in PALOMA-3, treatment with palbociclib + fulvestrant, after progression or relapse during previous ET, yielded a clinically important but not statistically significant survival improvement over fulvestrant monotherapy (median OS, 34.9 vs. 28.0 months; hazard ratio, 0.81; 95% CI, 0.64-1.03) (Turner et al., 2018). In a post hoc analysis of PALOMA trials, time to chemotherapy initiation was considerably longer for patients treated with palbociclib + letrozole (in PALOMA-2) and palbociclib + fulvestrant (in PALOMA-3) versus the respective non-palbociclib control groups (Rugo et al., 2022b). Further, an exploratory analysis of PALOMA-3 trial patients showed that patients who had not been treated with a prior chemotherapy for advanced breast cancer had improved OS with the palbociclib combination therapy versus the control group (median OS, 39.7 vs. 29.5 months; hazard ratio, 0.75; 95% CI, 0.56-1.01) (Rugo et al., 2021).

Data from at least 2 observational studies have shown possible OS benefits in relatively older patient populations. Results from P-Reality-X, a real-world evidence study conducted using data from the Flatiron electronic health record (median age, 70 years for palbociclib treatment group), also reported improved OS, specifically for patients receiving palbociclib + AI compared with AI alone. After stabilized inverse probability of treatment weighting, median OS (95% CI) is significantly longer among palbociclib compared with AI recipients (49.1 [45.2-57.7] vs. 43.2 [37.6-48.0] months; hazard ratio, 0.76 [95% CI, 0.65-0.87]; $P < 0.0001$) (Rugo et al., 2022a). In another study of older

patients (median age, 74 years for both the treatment arms: palbociclib + letrozole and letrozole alone), the palbociclib group was shown to have significantly better OS than the letrozole alone group (hazard ratio, 0.55 [95% CI, 0.42-0.72]; $P < 0.001$) (Rugo et al., 2023). In a recent observational study of an Medicare population of patients with diagnosis of *de novo* HR+/HER2- mBC using data from the Surveillance, Epidemiology, and End Results (SEER)-Medicare during an early period of CDK4/6 inhibitors use (2015-2017), Goyal et al. (2023) analyzed the effect of the CDK4/6 inhibitors (as a class) on OS and reported that combination therapy with ET and a CDK4/6 inhibitor is independently associated with improved OS compared with ET alone (hazard ratio, 0.59; 95% CI, 0.42-0.82). The majority ($\geq 90\%$) of patients in the CDK4/6 inhibitor group (median age, 70 years) in this study were taking palbociclib (Trapani and Mayer, 2023).

Because the evidence from real-world populations are often underrepresented in clinical trials (Lewis et al., 2003; Loree et al., 2019; Murthy et al., 2004; Talarico et al., 2004), and because 2 additional years of SEER-Medicare data have now become available allowing for more sample size and additional follow-up we seek to understand current data on potential survival benefits among the primary cohort of patients treated with palbociclib + AI compared with AI alone after *de novo* mBC diagnosis. A description of the SEER-Medicare database is provided in Section 2.1.

2.1 STUDY DESIGN

[figure not shown]
This study will encompass a retrospective cohort analysis using clinical and administrative claims data from the linked SEER-Medicare database (providing SEER data are available through 2019 and linked Medicare claims are available through 2020) for patients with diagnosis of HR+/HER2- mBC at initial presentation. The study will assess the rates of OS in patients 65 years or older with diagnosis of *de novo* mBC from 2015-2019 who initiated 1L systemic therapy with palbociclib + AI or AI alone following the first approval of palbociclib in February 2015. **Figure 2-1** presents a graphical schema of the study design (drawn for a hypothetical patient and not to scale).

Based on the study schema presented below, the following key study definitions will apply:

- **De novo mBC diagnosis date window:** From 1 February 2015 through 31 December 2019
- **Study index date:** The date of 1L treatment initiation with palbociclib + AI or AI alone after the *de novo* mBC diagnosis
- **Case selection window:** From 1 February 2015 through 30 June 2020 – for the date of 1L treatment initiation (study index date)

- **Baseline period:** The 6-month period before the study index date (to assess patient baseline demographic and clinical characteristics)
- **Study follow-up:** All patients will be followed from their study index date through the earliest of the following: death, disenrollment from Medicare Part A (hospital insurance), Part B (medical insurance), or Part D (prescription drug insurance), enrollment in a health maintenance organization (HMO) plan, or end of the study database (31 December 2020).
- **Overall study period:** From 1 August 2014 (to allow up to 6 months of look back period for any patient with index date in February 2015) through 31 December 2020 (accounting for a minimum 6 months of potential follow-up for any patient with index date in June 2020).

Figure 2-1. Study Design Schematic (Depiction for a Hypothetical Patient)

AI = aromatase inhibitor; HER2- = human epidermal growth factor receptor 2-negative; HR+ = hormone receptor-positive; mBC = metastatic breast cancer.

Note: Figure not drawn to scale.

Study Population

The study population will represent Medicare beneficiaries (men or women) with diagnosis of HR+/HER2- mBC at initial presentation (i.e., de novo), as identified in the SEER-Medicare database.

Data Source

The SEER-Medicare database is composed of 2 large population-based sources of data that provide detailed information about Medicare beneficiaries with cancer: (1) the SEER registry data that contain information about an incident cancer diagnosis and (2) linked Medicare data that contain longitudinal information on Medicare enrollment and

specific healthcare services received in different settings (e.g., hospitals, physician offices, outpatient clinics, nursing homes), as well as prescription drug utilization. The linkage of these 2 data sources results in a unique source of information that can be used for an array of epidemiological research, including health services use and survival outcomes, among older patients with cancer in the United States (US) Medicare population.

The SEER registries are part of the SEER Program, which is an epidemiologic surveillance system consisting of population-based tumor registries in certain states and metropolitan areas designed to track cancer incidence and survival in the US. The SEER registries collect information on nearly all (98%) newly diagnosed cancer cases, including breast cancer, in persons residing in SEER areas. SEER areas have been shown to be nationally representative (Nattinger et al., 1997) and the 21 registries represented in the SEER data linkage available for this study (SEER-21) capture over one-third (35%) of the total US population (Enewold et al., 2020). In contrast to the entire population of the US, the SEER Program encompasses a population that displays greater racial and ethnic diversity, along with a higher representation of individuals facing economic disadvantages (Enewold et al., 2020).

The SEER registry data released as part of SEER-Medicare are included in a customized file known as the SEER-Medicare Cancer file. The information collected on each SEER-reported cancer diagnosis includes patient-level demographic characteristics, date of diagnosis, clinical data about the tumor (e.g., stage, grade, size, estrogen receptor [ER] status, progesterone receptor [PR] status, and HER2 status), and cause and date of death. Linkage with Medicare data provides a database of persons generally aged 65 years and older with detailed information on incident cancer linked with comprehensive longitudinal healthcare utilization data from Medicare fee-for-service. In SEER-Medicare, the Medicare date of death information is collected from multiple sources, including the Social Security Administration (SSA), Railroad Retirement Board, and Medicare Common Working File; the Medicare date of death information is known to be complete for the given enrollment year (e.g., 2020 enrollment data will capture deaths occurring in 2020). Because almost all (99%) Medicare deaths are validated (98% through SSA), the vital status information available in the linked SEER-Medicare data make it one of the most authoritative data sources to examine survival outcomes in Medicare beneficiaries with an incident of cancer diagnosis in the US.

The linkage of SEER-Medicare data is managed by the National Cancer Institute (NCI), in collaboration with the contributing SEER registries and the Centers for Medicare & Medicaid Services. Investigators must submit a detailed application to the NCI for obtaining access to the required study data, which must be used under the terms of a data use agreement. Based on the most recent data linkage by the NCI, released in December

2022, SEER data are linked with Medicare patients aged ≥ 65 years with an incident (*de novo*) cancer diagnosis from 1999-2019, with linked claims and survival data available through 2020. The reason for the 3-year gap between cancer diagnosis and integration into the SEER-Medicare database stems from a 2-year period required for complete case reporting to the SEER Program, coupled with one extra year to process the data linkage. Information contained within the linked Medicare claims data, including dates and types of treatment utilization (including prescription drugs), make it possible to retrospectively “follow” patients after the date of their initial diagnosis reported in the SEER registry. Additional details on the structure, content, and application of the SEER-Medicare data can be found in the literature (Enewold *et al.*, 2020; Warren *et al.*, 2002).

2.2 STUDY OBJECTIVES

[figure not shown]
Following the work of Goyal *et al.* (2023), this retrospective, noninterventional study aims to assess OS in Medicare patients with HR+/HER2- *de novo* mBC who initiated 1L treatment with palbociclib + AI combination therapy versus AI alone. Specifically, the key objectives of this study are as follows:

Primary objective:

- To compare OS of 1L palbociclib + AI versus AI alone for women or men with *de novo* HR+/HER2- mBC in the SEER-Medicare database who are ≥ 65 years old

Exploratory objectives:

CCI

- To measure time to chemotherapy, if enough follow-up time is available to assess this measure.

3 HYPOTHESES AND DECISION RULES

The primary objective of this study is to demonstrate superiority of palbociclib + AI over AI monotherapy in prolonging OS for women and men aged ≥ 65 years with HR+/HER2- mBC as 1L treatment in the US clinical practice setting. The study is designed to test the null hypothesis $H_0: \lambda \geq 1$ versus alternative hypothesis $H_a: \lambda < 1$, palbociclib + AI cohort vs. AI monotherapy cohort, where λ stands for the hazard ratio.

PFIZER CONFIDENTIAL

4 ANALYSIS SETS/POPULATIONS

The patient section criteria that define the study population or analysis set are described in this section.

4.1 FULL ANALYSIS SET

Inclusion Criteria

Patients must meet all of the following inclusion criteria to be eligible for inclusion in the study:

1. *De novo metastatic (stage IV) disease at initial breast cancer diagnosis during 2015-2019 (Howlader et al., 2018):*
 - *Incident breast cancer diagnosis will be identified using the SEER Site Recode 26000, which includes cases classified as “breast” according to the International Classification of Diseases for Oncology, 3rd Edition codes: C50.0-C50.9, excluding histology codes 9050-9055, 9140, and 9590-9992 (National Cancer Institute, 2023b).*
 - *Staging at diagnosis will be determined using criteria applicable during the specific period. Specifically, the American Joint Committee on Cancer (AJCC) staging 7th edition variable will be used to classify diagnoses in year 2015, the derived SEER combined stage group variable will be used to classify diagnoses in years 2016-2017, and the derived Extent of Disease (EOD) stage group variable will be used to classify diagnoses in years 2018-2019.*
2. *Age \geq 65 years at diagnosis*
3. *“Age” as the reason for Medicare entitlement*
4. *Breast cancer recorded as the first cancer (coded as tumor sequence “1”) or the only cancer (coded as tumor sequence “0”) confirming no evidence of another, previous primary cancer diagnosis.*
5. *HR+/HER2- molecular subtype at diagnosis, using the SEER breast subtype variable (defined according to ER/PR and HER2 status)*
6. *Initiated 1L systemic therapy with a CDK4/6 inhibitor + AI or AI alone*
 - *Subsequently, and differing from Goyal et al. (2023), to assess the primary objective, the study cohort will be restricted to patients initiating 1L therapy with palbociclib + AI or AI alone within 6 months of mBC diagnosis:*
 - *It is assumed that most patients will initiate a systemic treatment within a few months of the diagnosis, and those who did not receive treatment*

PFIZER CONFIDENTIAL

within 6 months may have meaningful unobserved characteristics that likely influenced their treatment decisions.

7. *To ensure complete data for identifying the 1L of therapy, patients will be required to have continuous enrollment in Medicare Parts A and B and have prescription drug coverage (Part D) with no HMO participation from date of diagnosis until they initiate the 1L therapy, and they are allowed up to 6 months to initiate first-line therapy.*
8. *Continuously enrolled in Medicare Parts A and B with no HMO participation for ≥ 6 months before the index date*
 - *Because HMOs are not obligated to provide information about healthcare encounters (i.e., administrative procedure and diagnosis codes) to the Medicare system, patients who were enrolled in an HMO during study period may have incomplete data on service utilization, which may affect the accuracy of measurement for comorbid conditions and receipt of systemic therapy lines.*

Exclusion Criteria

Patients will be excluded if their mBC diagnosis was first recorded in a death certificate or at the time of autopsy.

4.2 SAFETY ANALYSIS SET

Not applicable.

4.3 OTHER ANALYSIS SET

Not applicable.

4.4 SUBGROUPS

To help better explain the results and to generate additional contextual data, subgroup analyses may be performed. As exploratory analyses, these subgroups may include age groups, metastatic sites, receipt of subsequent treatments, and other patient characteristics as appropriate, and the analyses will be conducted based on availability of the data and adequate sample sizes.

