5.1 EFFICACY/EFFECTIVENESS ENDPOINT(S)

As the primary endpoint, OS will be defined as time in months from initiation of 1L therapy to death from any cause. For details on endpoint definition, please refer to [Table 5-1](#).

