5.5 EXPOSURE VARIABLES AND COVARIATES

The exposure and other covariates to be analyzed as part of the study objectives and associated definitions are described in [Table 5-2](#). For covariates, categories may be further combined if appropriate for statistical purposes.

Table 5-2. Definitions of Exposure Variables

Variable	Role/objective	Definition
Exposure variables		
1L treatment type	Primary	
Patients initiating 1L therapy with one of the following regimens (to be identified in the Prescription Drug Event file using the generic drug names and HCPCS procedure codes, as applicable):
 
 • Palbociclib + AI • AI alone 
AI will include the following individual agents:
 
 • Anastrozole (HCPCS code: S0170) • Letrozole (HCPCS code: N/A) • Exemestane (HCPCS code: S0156) 
Therapy line definition: For each patient, the 1L therapy will be defined as all agents administered within a 60-day period after treatment initiation. The 1L therapy will start on the date the first agent will be

PFIZER CONFIDENTIAL

Variable	Role/objective	Definition
		administered (or filled) and will be considered to have ended upon occurrence of the earliest of any of the following: treatment switch to a new regimen or a gap of more than 90 days in administration or refill of any of the 1L regimen drugs. The start and end dates of the second and subsequent therapy lines will be defined in a similar fashion. The rules defining "treatment switch to a new regimen" are presented in Appendix 1.
Subsequent treatment	Exploratory	All subsequent treatment lines for patients initiating 1L therapy with palbociclib + AI or AI alone, including a description of treatment switch from AI alone to palbociclib + AI.
Control variables/covariates		
Tumor grade at diagnosis	Clinical characteristic (assessed at mBC diagnosis)	The tumor grade will be summarized as below: 
 • Grade 1 (lowest grade; well differentiated) • Grade 2 • Grade 3 • Grade unknown

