As the first step in implementation of PS-based methods (IPTW and PSM), the PS (i.e., the estimated probability of treatment assignment) will be obtained from a logistic regression model where the treatment assignment (treatment vs. control) will be regressed on a set of covariates or confounders. The baseline covariates or control variables that will be considered for adjustment in the multivariable logistic regression for deriving treatment probabilities (i.e., PSs for IPTW and PSM) are described earlier in [Table 5-2](#). The following variables will be included in the model: age group, race, year of mBC diagnosis, marital status, geographic status of residence, median household income, LIS coverage, tumor grade at initial diagnosis, involvement of metastatic sites at initial diagnosis (bone, brain, liver, and lung as independent binary variables), and NCICI score category. If any covariates are identified to have missing data, they may be coded as “missing” or “unknown” and included as categorical variables in the model.

Covariate Balancing

The following process will be implemented to determine whether there is sufficient overlap between the patient populations of the 2 treatment cohorts:

- Compute the standardized mean difference in PS for each level of each baseline covariate
- Graphically assess differences in the full distribution of each covariate between 2 treatment cohorts
- An absolute standardized mean difference < 0.1 indicates negligible difference and is considered a good balance

Covariate balance will be examined using both IPTW and PSM techniques as described below. Subsequently, depending on the quality of balance, the endpoint (OS) may be assessed using one or both techniques (Austin, 2014; Buchanan et al., 2014).

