9 APPENDICES

9.1 APPENDIX 1: RULES FOR DEFINING CHANGE IN THERAPY LINE

Condition	Rule
Switch to a completely new agent or combination of agents	Change in therapy line
Switching between CDK4/6 inhibitors (e.g., palbociclib to ribociclib or abemaciclib)	Change in therapy line
Therapy suspended for greater than 90 days	Change in therapy line
Addition of a new agent to an existing treatment regimen*	Change in therapy line
Removal of an agent from a combination regimen	Not a change in therapy line
Exception to switching within the same treatment class	
Anastrozole to letrozole (or vice versa)	Not a change in therapy line
Anastrozole to exemestane (or vice versa)	Not a change in therapy line
Letrozole to exemestane (or vice versa)	Not a change in therapy line

CDK4/6 = cyclin-dependent kinase 4 and 6.

** A treatment regimen is defined as combination of all agents administered within a 30-day period from the date of initiation of the first agent, with the exception of CDK4/6 inhibitors, for which a 60-day period will be allowed to account for insurance coverage delays. Addition of a new agent after 30 days (or 60 days for CDK4/6 inhibitors) will be considered a change in therapy line. A given therapy line will be considered to have ended upon occurrence of the earliest of any of the following: switch to a new treatment regimen or a gap of more than 90 days in administration or refill of any of the first line regimen drugs.*

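### SAP 4.4 allows an optional subgroup defined by later treatment, known only after the index date; if between-arm survival hazard ratios are estimated within it, they can be biased

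*SAP*

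**What the plan says.** SAP 4.4 describes optional, exploratory subgroup analyses meant to help explain the results, and says that "these subgroups may include age groups, metastatic sites, receipt of subsequent treatments, and other patient characteristics as appropriate". It names no endpoint, contrast or model for them, and does not say whether they are weighted.

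The time origin is set elsewhere. In SAP 5.1, "OS will be defined as time in months from initiation of 1L therapy to death from any cause". SAP Table 5-2 defines subsequent treatment as "All subsequent treatment lines for patients initiating 1L therapy with palbociclib + AI or AI alone", with an exploratory role. Under the claims rules in SAP Appendix 1, a 1L line ends at a switch of regimen or at "a gap of more than 90 days in administration or refill of any of the first line regimen drugs".

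The propensity model in SAP 7.3 uses baseline covariates only: "The following variables will be included in the model: age group, race, year of mBC diagnosis, marital status", followed by socioeconomic, tumour and comorbidity variables. The switching analysis in SAP 7.6 is optional and concerns later CDK4/6 inhibitor use in the AI cohort. The subgroup variables named in SAP 7.5 and Protocol 9.7.3 do not include later treatment.

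**The concern.** A subgroup used to compare treatments should be identifiable at time zero. This one is not. To count as a recipient of later treatment, a patient must survive and remain enrolled until a second line starts. Patients who die or are censored early become non-recipients by construction. If 1L treatment changes when or whether a second line starts, the two arms are sorted into these strata differently, and a within-stratum hazard ratio mixes that sorting with any effect on survival.

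The SAP's own background makes arm differences plausible. It reports longer progression-free survival with CDK4/6 inhibitor + AI, and for the palbociclib trials it says that "time to chemotherapy initiation was considerably longer for patients treated with palbociclib + letrozole". It also calls 2015-2017 an early period of CDK4/6 inhibitor use; against a fixed end date of 31 December 2020, that could mean shorter follow-up on palbociclib.

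At stake is the reading of an exploratory result. With no OS effect at all, the split could show an apparent benefit or an apparent harm, and it would be offered as help in explaining the main finding.

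**Working it through.** The plan gives no figure for this subgroup, so there is none to reproduce. The check asks what within-stratum hazard ratios (palbociclib + AI versus AI alone) look like when the true OS hazard ratio is 1.

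**From the documents.** Index dates run from 1 February 2015 to 30 June 2020 and the database ends on 31 December 2020 (SAP 2.1), so potential follow-up is 6 to 71 months. Median OS of 43.2 months is the weighted AI-alone figure from the electronic health record study cited in SAP 2.

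**Assumed.** That this median applies in SEER-Medicare; exponential times; follow-up uniform over 6-71 months with no disenrollment; the times to next line; their correlation with survival (Gaussian copula); the share taking up a next line; and no effect of later treatment on death. The documents supply none of these.

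**Hand check: correlation 0, full uptake, no end of follow-up.** The first of death and next line has median 1/(1/m + 1/43.2), where m is the median time to next line.
- AI alone, m = 14: 1/(0.0714 + 0.0231) = 10.6 months.
- Palbociclib + AI, m = 24: 1/(0.0417 + 0.0231) = 15.4 months.

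Recipients therefore have a guaranteed survival period with median 10.6 versus 15.4 months, and identical survival after it. Non-recipients die at rates proportional to 1/10.6 and 1/15.4, a hazard ratio of 10.57/15.43 = 0.69. Both strata favour palbociclib although it does nothing to survival.

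**Simulation with 6-71 months of follow-up.** At least 600,000 patients per setting; univariate Cox; overall hazard ratio 0.99-1.01; standard error of the log hazard ratio about 0.004-0.010. A range shows agreement between separate runs. Uptake is 100% unless stated.

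| AI alone vs palbociclib + AI | Received | Not received |
|---|---|---|
| 14 vs 24 months, correlation 0 | 0.90 | 0.75 |
| same, correlation 0.3 | 0.95-0.96 | 0.78-0.79 |
| same, correlation 0.5 | 0.99-1.01 | 0.83 |
| same, correlation 0.7 | 1.07 | 0.95 |
| 20 vs 14 months, correlation 0 | 1.08 | 1.23 |
| 14 vs 14, correlation 0 vs 0.3 | 1.17-1.18 | 0.79 |
| 14 vs 14, correlation 0.3 vs 0 | 0.85 | 1.25-1.27 |
| 14 vs 14, correlation 0, palbociclib follow-up cut to 6-48 months | 1.06-1.07 | 0.81-0.82 |
| 14 vs 14, correlation 0, uptake 75% vs 50% | 1.00-1.01 | 0.82-0.83 |
| 14 vs 14, correlation 0.7, uptake 75% vs 50% or the reverse | 0.99-1.01 | 0.99-1.00 |
| 14 vs 14, all else equal | 1.00 | 1.00-1.01 |

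Three things follow. Each stratum can move either way. Bias in the same direction in both strata weakens as correlation rises: in recipients it is largely gone by 0.5, and at 0.7 the strata point in opposite directions. And unequal uptake can leave both strata near 1.00.

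**Do other parts of the plan correct this?** Baseline weights balance what is known at the index date. Because they include year of diagnosis they could, if applied, narrow a difference in potential follow-up, but not differences in disenrollment, HMO entry or time to next line. The SAP 7.6 analysis asks what OS would have been without later CDK4/6 inhibitors in the AI cohort. It does not govern a split on any later treatment in both arms.

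**The case against.** The strongest reply is that SAP 4.4 never says a between-arm hazard ratio will be computed here. The analyses are optional and exploratory, and Table 5-2 treats later lines partly as something to describe. A descriptive reading is plausible and would not carry this bias. That stands, and it is why the point is conditional. It does not remove the point: the item sits in a list of subgroups beside age and metastatic sites, and nothing in SAP 4.4 limits it to description.

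A second reply is that later treatment is handled elsewhere. SAP 7.3 refers the reader to SAP 7.6 for adjustment, SAP 7.5 does not name this subgroup, and the exploratory methods in SAP 7.4 are redacted. It is fair that a safeguard there cannot be ruled out. The visible text has none, and SAP 7.6 answers a different question.

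A third reply is that the numbers rest on assumptions. They do. They show that the problem can be material; they do not estimate it for this study.

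A reader might infer that any arm difference must produce bias, or that the hazard ratios are near 1 only when everything is equal between arms. The unequal-uptake rows at correlation 0.7 show otherwise. A reader might also infer that the bias favours palbociclib. The documents do not support that: line ends are set by claims rules, and no time to next line, uptake or palbociclib use by year is given. Nor does SAP 4.4 contradict SAP 7.5 or Protocol 9.7.3, because all three lists are illustrative.

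**Conclusion.** The concern holds in conditional form. The subgroup is defined after the index date while OS runs from 1L initiation. Between-arm OS hazard ratios within it, if estimated, can be biased by immortal time and selection, and would not estimate the effect of 1L treatment in any population identifiable at the start. Neither the baseline weights nor the switching analysis corrects this.

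Size and direction cannot be fixed from the documents. Under the assumptions listed, with no OS effect, the illustrations range from clear apparent benefit in both strata to clear apparent harm in both, with near-zero bias in some unequal settings. The issue is minor: the analysis is optional and exploratory, and the primary comparison is untouched.

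**What to change.** Delete the item on subsequent treatments from SAP 4.4, or limit it to a descriptive summary with no between-arm hazard ratio. Add one sentence saying that subgroups for treatment comparisons use only characteristics measured at or before the index date, in line with the variables named in SAP 7.5 and Protocol 9.7.3. Keep the description of later lines in Table 5-2. If the effect of later therapy on OS is itself of interest, specify a method that treats it as time-varying.

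The cost is one phrase removed or qualified and one sentence added. What is lost is one optional exploratory split that could not be interpreted as a treatment comparison.
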